### 2.2.1 Clinical

Three clinical studies of bimekizumab have been completed: UP0008 in 39 subjects with mild to moderate plaque psoriasis, RA0124 in 30 healthy volunteers, and PA0007 in 53 subjects with psoriatic arthritis. Two studies (RA0123 and UP0031) are ongoing in subjects with moderate to severe rheumatoid arthritis and in healthy subjects, respectively.

UP0008 was a Phase 1, single ascending dose study in adults with mild to moderate psoriasis affecting  $\leq 5\%$  BSA. In this blinded study, single doses of up to 640mg (approximately 8mg/kg in an 80kg adult) were evaluated without any safety concerns. A total of 26 subjects with psoriasis with less than 5% of body surface involvement were treated with a range of single iv doses from 8 to 640mg. There were no clinically relevant safety findings identified at any dose and all doses were well tolerated. The pre-specified exploratory assessment of disease activity showed clinically relevant and statistically significant improvements at the higher doses studied.

RA0124 was a Phase 1, open-label, parallel-group, single-dose study in healthy subjects. The primary objective of this study was to determine the absolute bioavailability of single sc doses of bimekizumab (80mg and 160mg). The secondary objectives were to evaluate the dose proportionality of bimekizumab 80mg and 160mg sc, and to evaluate the safety and tolerability of these sc doses and 160mg given by iv infusion. In RA0124, the absolute bioavailability was similar for the 2 doses tested (0.656 and 0.631 for the bimekizumab 80mg and 160mg sc doses, respectively). The PK of bimekizumab was linear in the tested dose range and the median  $t_{1/2}$  following sc administration was similar to that following iv administration (27.81 days and 28.25 days for bimekizumab 160mg sc and 160mg iv, respectively).

Bimekizumab has also been investigated in a Phase 1b, proof of concept, randomized, placebo-controlled, multiple dose study (PA0007). The primary objective of PA0007 was to assess the safety and PK of multiple dose administration of iv bimekizumab in subjects with psoriatic arthritis. Four active doses and a placebo were tested. Drug was administered as a loading dose at Week 0, and 2 additional doses were administered at Week 3 and Week 6. In each treatment group, subjects received a total of 3 doses of bimekizumab, administered every 3 weeks as shown below:

- 80mg loading dose followed by 40mg at Weeks 3 and 6

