**Table 5–1: Schedule of study assessments**

Protocol activity	Visit Week a	PS0018 Baseline	Open-Label Treatment Period											SFU b
			Wk 4	Wk 8	Wk 12	Wk 16	Wk 20	Wk 24	Wk 28	Wk 32	Wk 36	Wk 40	Wk 44	

BSA=body surface area; C-SSRS=Columbia-Suicide Severity Rating Scale; ECG=electrocardiogram; HADS=Hospital Anxiety and Depression Scale; IGA=Investigator’s Global Assessment; IGRA=interferon gamma release assay; IXRS=interactive voice or web response system; PASI=Psoriasis Area and Severity Index; Q4W=every 4 weeks; SFU=Safety Follow-Up; TB=tuberculosis; WD= withdrawal; Wk=week

a Visit windows of ±3 days from the first dose (Baseline) at all visits except SFU, which has a window of -3 and +7 days from scheduled visit date.

b The SFU Visit will occur 20 weeks after the last dose.

c Ensure that the informed consent for PS0018 was completed by the subject (must be done before any study assessments are performed for PS0018).

d To be performed prior to the first dose of open-label bimekizumab.

e Includes evaluation of signs and symptoms of active TB and risk for exposure to TB.

f The noted PS0018 Baseline assessments will be obtained at the final visit of PS0016 and do not need to be recorded on the case report form for this study.

g Vital signs (blood pressure, pulse rate, and temperature) are to be measured prior to blood sampling and prior to dosing, where applicable.

h The FSH test should only be performed on postmenopausal females who have been postmenopausal for ≥1 year and last menstrual cycle occurred <2 year ago.

i Pregnancy testing will be urine testing at all visits except SFU, which will be a serum test.

j It is recommended that the QuantiFERON TB GOLD test be performed.

k All blood samples are to be taken prior to dosing.

l Including assessment for the development of different forms of psoriasis at the SFU visit.

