### 4.4 Handling of measurements obtained at the withdrawal visit

Subjects who withdraw from the PS0018 study prematurely will be encouraged to return for the early WD visit and the SFU Visit, the latter at 20 weeks following the final dose of study medication.

The following rules will apply with regard to the inclusion of the results obtained at the early WD visit in the descriptive summaries:

- Any efficacy, PK, immunological and safety measurements conducted at the early WD visit should be included in the summaries for the respective scheduled visit, if the early WD visit occurs at the time of the next scheduled visit (within the tolerance window specified in the protocol). For example, if the early WD visit occurs on Day 28, the results would be summarized together with the Week 4 results.
- If the early WD visit does not correspond to the day of a scheduled visit, all assessments of the early WD visit should be mapped to the nearest scheduled visit, relative to the PS0018 Week 0 visit date, following the last scheduled visit where assessments are available.
- If the date of the early WD visit is equidistant between 2 scheduled visits at which no scheduled assessments were performed, the assessments from the early WD visit will be mapped to the earlier of these visits.
- If an EW visit mapping results in data being mapped to a visit where the specific assessment is not actually collected per the protocol schedule of assessments, these data will not be included in the summary statistics and will be listed only.
- The only exception to the above rule is for ADA (for both BKZ and CZP) assessments, in which all early withdrawal visit assessments will be assigned to the next scheduled visit at which ADA are assessed. The rationale for this is that ADA positivity is summarized over a given study period. As part of that summary, a table indicating the first visit at which ADA positivity is observed will be presented. In order to match the number of subjects who were ADA positive at specific visits with the overall positivity for the period, it is necessary to ensure that ADA positivity is attributed to a visit where ADA antibody assessments were performed.

Assessments from the EW visit will be displayed as the mapped visit and will be flagged in the by-visit data listings.

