For example, vital sign assessments are performed at PS0018 Weeks 0, 4, 8, 12, 16, 20, 24, 28, 32, 36, 40 and 44. If a subject discontinues on Day 37, and the previous vital sign assessment was done at Week 4 (Day 28), the nearest scheduled assessment (following the last visit at which assessments were available) would be Week 8 (Day 56). Therefore, the early WD visit assessment should be re-assigned to the Week 8 visit.

However, if a subject discontinues at Day 37, and the previous vital sign assessment was done at PS0018 Week 0, the early WD visit assessments would be re-assigned to the Week 4 (Day 28) visit, which would be the nearest scheduled visit relative to the PS0018 Week 0 visit date.

Different domains (eg vital signs, ECG, safety laboratory tests, PASI, IGA) from the same early WD visit may be re-assigned to different study visits depending on the study schedule of assessments, ie measurements obtained at the early WD visit can only be mapped to a scheduled visit at which the respective assessment was intended to be measured. Assessments from the early WD visit that are mapped to scheduled visits will be flagged in the data listings.

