## 9 PHARMACOKINETICS

There will be no calculation of PK parameters for this study. The analysis of PK data for this study will focus on the concentrations of bimekizumab only.

Individual blood sampling times and concentrations of bimekizumab will be listed by PS0016 randomized treatment group for the SS and will include the actual sampling time in weeks relative to the first PS0018 dose.

Individual concentrations will be summarized by PS0016 randomized treatment group at each scheduled visit based on the PK-PPS, using n, mean, median, SD, minimum, maximum, geometric mean, 95% CI for the geometric mean and geoCV (assuming log-normally distributed data).

Individual concentration versus time (week) profiles will be presented graphically in linear and semi-logarithmic scale with all subjects overlaid on the same plot (spaghetti plots) and separate plots for each treatment group. Geometric mean profiles of bimekizumab will also be presented on both linear and semi-logarithmic scale respectively with and without the corresponding lower and upper limit of the 95% CI for linear and semi-logarithmic plots respectively. Both treatment groups (PS0016 randomized treatment groups) will be overlaid on the same plot. All figures will include the LLOQ on the semi logarithmic plots.

The following rules will apply for PK data listings and summaries:

- Values below the LLOQ will be reported as BLQ
- Descriptive statistics of concentrations will be calculated if at most 1/3 of the individual data points are missing or are not quantifiable ie LLOQ. Values that are BLQ will be replaced by the numerical values of the LLOQ/2 in this instance. However, if  $n \leq 3$  or more than 1/3 of the individual data points are missing or are not quantifiable, then only n, minimum and maximum will be presented. The other descriptive statistics will be left blank.
- The 95% CI for the geometric mean should be left blank if the SD (or equivalently, the geoCV) is 0
- The geoCV will be calculated using the following formula where SD is the standard deviation from the log-transformed data

$$geoCV = [100 \times \sqrt{(e^{SD^2} - 1)}] \quad [9]$$

Additional rules for handling values that are BLQ are described in [Section 4.2.3](#).

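### SAP 4.4 maps early-withdrawal PK samples by calendar time alone, so some non-trough concentrations enter by-visit summaries that otherwise hold predose troughs

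*SAP*

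**What the plan says.** SAP 4.4 covers two cases. If the early-withdrawal visit falls in the window of the next scheduled visit, "Any efficacy, PK, immunological and safety measurements conducted at the early WD visit should be included in the summaries for the respective scheduled visit". If it does not, "all assessments of the early WD visit should be mapped to the nearest scheduled visit, relative to the PS0018 Week 0 visit date", counting only visits after the last one with data.

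Two further statements limit this. A bullet says that when the mapped visit does not collect the assessment in question, "these data will not be included in the summary statistics and will be listed only", with anti-drug antibodies as the only exception. The closing paragraph of the section says instead that "measurements obtained at the early WD visit can only be mapped to a scheduled visit at which the respective assessment was intended to be measured", and that different domains from one withdrawal visit may go to different visits.

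On sampling, Protocol Table 5–1 states "All blood samples are to be taken prior to dosing", and Protocol 10 repeats this for PK at dosing visits. Protocol 7.2 sets 24 to 32 days between doses. Protocol 8.11 gives the early-withdrawal visit the same assessments as Week 48, which include a PK sample.

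On analysis, SAP 9 states "Individual concentrations will be summarized by PS0016 randomized treatment group at each scheduled visit based on the PK-PPS", with geometric means, confidence intervals and mean profiles.

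**The concern.** A by-visit PK column is interpretable because every value in it was taken at about the same time after a dose. Mapping by distance from Week 0 ignores that time. A subject who leaves partway through a dosing interval contributes a value that is usually above trough. One who missed a dose before leaving contributes a value below it. The two errors run in opposite directions, so a reader of the table cannot allow for them.

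The protocol can produce such samples. Withdrawal criterion 6 in Protocol 6.3 asks for the withdrawal visit as soon as possible and no later than the next regular visit, so it may fall mid-interval.

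The SAP treats similar data differently elsewhere. SAP 4.3 keeps unscheduled post-dose measurements out of by-timepoint summaries, and SAP 4.4 gives antibodies their own reasoned rule. PK has neither protection. PK is a secondary objective, no PK parameters are calculated, and the by-visit summaries are therefore its main tabulated result.

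**Working it through.** **Inputs from the documents**
- Visits every 4 weeks from Week 0 to Week 48, with a ±3-day window; dosing at Weeks 0 to 44, giving 12 dosing intervals (Protocol Table 5–1; SAP 7).
- PK samples after Week 0 in the treatment period at Weeks 4, 8, 12, 16, 28, 40 and 48 (Protocol Table 5–1).
- Median half-life: "27.81 days and 28.25 days for bimekizumab 160mg sc and 160mg iv, respectively" (Protocol 2.2.1, single doses in healthy subjects).
- Up to 45 subjects, from a study randomised 2:1: 30 and 15 if all roll over.

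**Assumptions**
- Absorption rate ka between 0.15 and 1.0 per day; the documents give none.
- Full roll-over, with every subject contributing at the visit.

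**1. The SAP's own example.** It concerns vital signs: "If a subject discontinues on Day 37, and the previous vital sign assessment was done at Week 4 (Day 28"). Taking the nearest scheduled visit after the last one with data, with ties to the earlier, Day 37 maps to Week 8 (Day 56). If the last assessment was at Week 0, it maps to Week 4 (Day 28). Both agree with the SAP.

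**2. The same rule applied to PK.** PK is also scheduled at Weeks 4 and 8. Assume a dose at Week 4 on Day 28. The Day 37 sample is 37 − 28 = 9 days postdose and is summarised with the Week 8 troughs.

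**3. How many intervals are exposed.** Take a subject who attends every visit. Each 28-day interval has 21 days lying more than 3 days from a scheduled visit, so there are 12 × 21 = 252 off-window days.
- *Listed-only bullet.* The mapped visit is the end of the current interval. It collects PK at Weeks 4, 8, 12, 16, 28, 40 and 48: 7 × 21 = 147 days, and 147/252 = 58%. Samples mapped to Weeks 20, 24, 32, 36 or 44 are listed only.
- *Closing paragraph.* The sample moves on to the next PK visit, so all 252 days are exposed. For example, Day 116 is 4 days after a Week 16 dose (Day 112) and would be summarised at Week 28. Under the listed-only bullet it maps to Week 20 and is only listed.

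**4. Size for one sample.** Ratio to the 28-day trough at t days after the last dose.
- Mono-exponential decline: 2^((28 − t)/27.81).
- One-compartment subcutaneous model over the assumed ka range, after 2 or 12 doses, where absorption lowers the early ratios.

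| Days since last dose | Mono-exponential | With absorption |
|---|---|---|
| 9 | 2^(19/27.81) = 1.61 | 1.28 to 1.61 |
| 14 | 2^(14/27.81) = 1.42 | 1.28 to 1.42 |
| 21 | 2^(7/27.81) = 1.19 | 1.16 to 1.19 |
| 42 | 2^(−14/27.81) = 0.71 | 0.71 to 0.72 |
| 56 | 2^(−28/27.81) = 0.50 | 0.50 to 0.51 |

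**5. Effect on the visit's geometric mean.** With one such sample among n, the factor is ratio^(1/n).
- 9-day sample, n = 30: 1.28^(1/30) = 1.008 to 1.61^(1/30) = 1.016, so +0.8 to +1.6%.
- 9-day sample, n = 15: 1.28^(1/15) = 1.017 to 1.61^(1/15) = 1.032, so +1.7 to +3.2%.
- 56-day sample, n = 15: 0.50^(1/15) = 0.955, so −4.5%.

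**6. After the fix.** Limiting summarised withdrawal samples to 24 to 32 days since the last dose gives ratios from 2^(4/27.81) = 1.10 down to 2^(−4/27.81) = 0.91.

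**The case against.** The strongest case on the other side has five parts.

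- **The listed-only bullet already keeps many samples out.** This stands if that bullet governs PK: 5 of 12 intervals are then protected. Because antibodies are called its only exception, that may well be the intent. The closing paragraph reads otherwise, so the SAP does not settle it.
- **Many withdrawals are unaffected.** SAP 4.2 names failure to reach PASI50 as the expected source of missing data. PASI is scored before dosing at regular visits, so a withdrawal sample taken then is a true trough. This stands.
- **The data evaluation meeting can deal with it.** SAP 3.4 gives that meeting a say over withdrawals, and SAP 3.6 allows exclusion at single visits, though in the context of incorrect treatment. Neither sets a timing criterion. The PK-PPS removes only important deviations that affect PK, and withdrawing as the protocol directs is not one. This does not cure the gap.
- **The reader can see the timing elsewhere.** SAP 9 and 10 provide individual profiles, actual sampling times and a listing with days since the last dose, and mapped values are flagged. This stands: a reader might infer that the by-visit means are the only PK output, and they are not.
- **The shift is small beside other variation.** The columns follow the PS0016 groups, so after Week 12 they may pool 160mg and 320mg recipients. If the geometric CV were 30 to 50% (an assumption), the upper 95% limit at n = 15 would already lie about 18 to 30% above the mean. This stands and bears on severity.

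A reader might also infer that the off-trough values come mostly from subjects leaving for safety reasons. The documents give no withdrawal counts by reason, and SAP 4.2 points to lack of response.

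**Conclusion.** The gap is real and minor. SAP 4.4 lets some early-withdrawal concentrations into by-visit PK summaries without regard to time since the last dose, and nothing in SAP 4.2.3, SAP 9 or the PK-PPS definition prevents it. SAP 4.4 also contains two mapping rules that give different results for PK.

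The 1.61 ratio at 9 days is the upper end, since it assumes that absorption is complete. The percentage shifts assume that all 45 subjects roll over; with fewer contributors at a visit, one sample weighs more. Larger shifts can be constructed: three 9-day samples in a group of 15 would raise the geometric mean by 5.1% (1.28^(3/15)) to 9.9% (1.61^(3/15)). That needs a fifth of the group to leave off-window before the same visit, and nothing in the documents suggests it. Nor do the documents support reading the SAP's Day 37 case as a PK example: it is about vital signs, and the Day 28 dose is assumed here.

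The primary safety analysis and the efficacy results are not affected.

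**What to change.** In SAP 4.4 and 9, state that an early-withdrawal concentration enters by-visit PK summaries and mean plots only if it was drawn 24 to 32 days after the last dose, the protocol's own dosing-interval tolerance. Otherwise it is listed with days since last dose, which the combined concentration and antibody listing in SAP 10 already reports. This keeps predose withdrawals at regular visits in the tables.

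In SAP 4.4, also state whether the listed-only bullet or the closing paragraph governs PK.

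The cost is a few sentences and one programming filter. The downside is that a few withdrawal samples move from tables to listings. The filter does not reach a subject who stops dosing but keeps attending ordinary scheduled visits; that is not a withdrawal-mapping question.

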## 4.5 Interim analyses and data monitoring

There will be no interim analysis.

An independent Data Monitoring Committee (DMC) will be convened to periodically review and monitor safety data and to advise UCB accordingly. A separate cardiovascular adjudication committee and neuropsychiatric adjudication committee will also review the relevant data for assessment of cardiovascular and potential suicide events respectively, and will provide additional advice to UCB.

The detailed role, scope, responsibilities and complete procedures as well as the identity of the DMC members will be described in a separate DMC Charter. The details regarding the outputs to be produced and the analyses to be performed for the DMC review will be provided in a separate DMC SAP.

A separate Charter will be written for each of the cardiovascular and neuropsychiatric adjudication committees.

#### **4.6 Multicenter studies**

Individual center results will not be displayed.

#### **4.7 Multiple comparisons/multiplicity**

Not applicable.

#### **4.8 Use of an efficacy subset of subjects**

Not applicable.

#### **4.9 Active-control studies intended to show equivalence**

Not applicable.

#### **4.10 Examination of subgroups**

Not applicable.

### **5 STUDY POPULATION CHARACTERISTICS**

#### **5.1 Subject disposition**

The number and percentage of subjects who were enrolled into the PS0018 study, subjects who completed or prematurely discontinued the PS0018 study, as well as the reason for discontinuation will be presented by PS0016 randomized treatment group and for all subjects, based on the SS. Subjects withdrawn from the study due to not achieving PASI50 at week 12 or later will be presented in the summary under primary reason for discontinuation in the category 'Lack of efficacy'.

The number and percentage of subjects who discontinued due to AEs will be separately summarized by PS0016 randomized treatment group for all subjects, based on the SS.

The number and percentage of subjects included into each of the analysis sets will be summarized by PS0016 randomized treatment group and for all subjects based on the ES (all subjects screened). Percentages will be based on the SS for the purpose of this summary.

Finally, screen failure reasons will be listed, including glossary and summarized, based on the ES.

A subject who completed the study is defined as a subject having completed the 48 weeks of Open-Label Treatment Period.

In addition, the following listings will be presented by PS0016 randomized treatment group:

- Subject disposition (all subjects screened [ES])
- Study discontinuation (SS)
- Visit dates (SS)
- Subject analysis sets (all subjects screened [ES])

The listing of subject disposition will include the date of informed consent, date and time of first and last dose of study medication in PS0018, date of premature termination (and primary reason) and date of final contact.

The listing of study discontinuation will include the reason for discontinuation and the total days on study medication relative to first dose in PS0018.

A summary of the dose adjustment grouping (nonadjuster, single adjuster, and multiple adjuster) will be presented by the FAS and SS, respectively.

The number of days on PS0018 study medication will be calculated as follows:

$$\text{Number of Days on Study Medication} = (\text{Date of Last Dose Received} - \text{Date of First Dose Received}) + 1 \quad [4]$$

## 5.2 Protocol deviations

Important protocol deviations will be identified and classified by the deviation types listed in the protocol deviation specification document. A listing of all important protocol deviations will be presented for all subjects by PS0016 randomized treatment group and will include the deviation type and description. The number and percentage of subjects with important protocol deviations will be summarized by PS0016 randomized treatment group and for all subjects for each deviation type, based on the SS.

## 6 DEMOGRAPHICS AND OTHER BASELINE CHARACTERISTICS

### 6.1 Derivation of variables

Demographic and baseline characteristics are based on data recorded at the PS0016 Baseline visit.

#### 6.1.1 Calculation of body mass index

The body mass index (BMI) in kg/m^2 is calculated based on the height (in m) and the weight (in kg) using the following formula:

$$\text{BMI} = \text{Weight}/(\text{Height})^2 \quad [5]$$

The BMI will be reported to 1 decimal place.

### 6.1.2 Classification of age categories

Age will be classified into categories based on requirements for European Union Drug Regulating Authorities Clinical Trials (EudraCT) and clinicaltrials.gov reporting.

For the EudraCT reporting, the categories will include:

- 18 to <65 years
- 65 to <85 years
- $\geq 85$  years

For the clinicaltrials.gov reporting, the categories will include:

- $\leq 18$  years
- 19 to <65 years
- $\geq 65$  years

